PLANNED INTERIM ANALYSES	No interim analyses planned given the short-term duration of the study, the established safety of the treatment, and the lack of randomization (so no ability to compare rates of AE's between active and placebo treatment).
STATISTICS Primary Analysis Plan	Correlations between changes in mean levels of urinary metabolites and changes in mean behavioral measures (0 to 3 months) will be done using a spearman rank correlations test using STATA. We prospectively define correlations with an absolute value of ≥ 0.6 to be potentially involved in the mechanism of action. All metabolites with this correlation will be mapped to known metabolite pathways to examine pathway changes.
Rationale for Number of Subjects	We are recruiting all children currently enrolled at Oak Hill School (current enrollment = 36). We anticipate that we will enroll 20 students in the current study, but we will allow up to 40 (if school enrollment increases).

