13.1 Analysis of Primary Endpoint

The primary analysis in the study is the correlation between the mean change in each urinary metabolite and the mean change in participant behavior as measured by the ABC using the spearman rank correlation test in Stata. The primary outcome measure is the correlation between urinary metabolites and the total ABC score.

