13.3 Sample Size

The study is designed to detect a correlation coefficient (Pearson's r) between the mean urinary metabolite change and the mean behavioral measure change of 0.6, which is considered to indicate a moderate-to-strong correlation. Using a two-sided alpha of 0.05 and a Beta of 0.1 (90% power), our required sample size is 25 participants to detect this degree of correlation. Since we may incur up to 20% dropout (5 participants), our target sample size is 30 participants, but we will allow up to 40 to provide the study opportunity to all children enrolled in the target school (Oak Hill School).

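### Section 13.3 takes the 20% dropout allowance from the required 25 rather than from the children enrolled, so at full 20% dropout the target of 30 keeps 24, one short of the plan's own requirement

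*Combined protocol and SAP*

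**What the plan says.** Section 13.3 (Sample Size) gives all the inputs. The effect size is stated as "The study is designed to detect a correlation coefficient (Pearson's r) between the mean urinary metabolite change and the mean behavioral measure change of 0.6". The error rates follow: "Using a two-sided alpha of 0.05 and a Beta of 0.1 (90% power". From these the section concludes that "our required sample size is 25 participants to detect this degree of correlation".

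The next sentence turns this requirement into an enrolment figure: "Since we may incur up to 20% dropout (5 participants), our target sample size is 30 participants". It goes on to set a ceiling: "but we will allow up to 40 to provide the study opportunity to all children enrolled in the target school".

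The synopsis, under the rationale for the number of subjects, gives a different expectation: "We anticipate that we will enroll 20 students in the current study, but we will allow up to 40 (if school enrollment increases".

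**The concern.** The 25 comes from a power formula, so it is the number of children who must be in the analysis. An allowance for dropout should start from the number enrolled, because those are the children who can drop out. Section 13.3 converts 20% into 5 children, which is 20% of 25, and adds them to 25. The intended safeguard is that 25 remain even at the worst loss the plan foresees. At exactly that loss, the stated target does not provide it. What is at stake is whether the enrolment target, the dropout rate and the 90% power in one paragraph can all be true together.

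**Working it through.** **Inputs, all from section 13.3:** r = 0.6 against 0, two-sided alpha 0.05, power 90%, required number 25, maximum dropout 20% (given as 5 children), target 30, ceiling 40.

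**Step 1. Reproduce the 25.** The Fisher z formula is n = ((z for 0.975 + z for 0.90) / atanh(r))² + 3. With atanh(0.6) = 0.6931:

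n = ((1.960 + 1.282) / 0.6931)² + 3 = 24.87, rounded up to 25.

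The plan's figure is reproduced. The one-sided version gives 21 and the two-sided version at 80% power gives 20, so the stated inputs are the ones used.

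**Step 2. Reproduce the 30.** 25 × 1.20 = 30, and 25 × 0.20 = 5. The stated 5 confirms that the percentage was taken of 25.

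**Step 3. Apply 20% dropout to the target.** 30 × 0.20 = 6 lost; 30 − 6 = 24 kept, one below 25. Five losses from 30 is 5/30 = 16.7%, which is the largest loss that 30 can absorb.

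**Step 4. Inflate correctly.** 25 / (1 − 0.20) = 31.25, rounded up to 32. Check: 32 × 0.8 = 25.6, whereas 31 × 0.8 = 24.8. Counted in whole children, 31 with 6 losses (6/31 = 19.4%) would also leave 25. The usual rounding gives 32, and 30 falls short on either count.

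**Step 5. Effect on power.** By the same formula, power = Φ(0.6931 × √(n − 3) − 1.960):

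- n = 25: Φ(0.6931 × √22 − 1.960) = Φ(1.291) = 90.2%
- n = 24: Φ(0.6931 × √21 − 1.960) = Φ(1.216) = 88.8%

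The loss is 1.4 percentage points.

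**Step 6. Check without the approximation.** The Pearson t-test was simulated with bivariate normal data, r = 0.6 and 200,000 replicates. Power was 91.3% at 25 and 90.1% at 24. The simulation error is about √(0.9 × 0.1 / 200,000) = 0.07 points, so power at 24 is 90% for practical purposes.

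**Step 7. Separate the Spearman question.** Section 13.1 plans a Spearman test. In the same simulated data its power was 86.7% at 25 and 85.0% at 24. Of the 5.0 points between 90% and 85.0%, 3.3 are already present at 25, where the dropout allowance plays no part. Moving from 25 to 24 accounts for the other 1.7.

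**The case against.** The arithmetic slip is hard to dispute, but its importance can be.

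- **The shortfall is conditional.** The 20% is a maximum, and the target is not a ceiling because up to 40 may enrol. The shortfall of one needs the full loss at exactly 30 enrolled. This stands, and it rules out the reading that a target of 30 will in fact yield 24. The permission to reach 40 does not repair the figure, however: it exists to offer the study to all pupils and does not make 32 the target.
- **Stopping the supplement need not mean loss.** Section 11 asks children who discontinue to continue the scheduled outcome assessments. This helps only in part. The primary analysis also needs the month 3 urine sample (sections 8.2 and 9.4), which that sentence does not mention, and section 11.1 allows full withdrawal.
- **Power for Pearson's r is hardly affected.** At 24 the simulated t-test still has about 90% power. This stands. The fall below 90% appears only with the Fisher z approximation, although that is the formula that gives the plan's 25.
- **Little turns on one child.** The study has a single arm and describes itself as exploratory. Recruitment is open to one whole school, and the synopsis flags metabolites by an absolute correlation of at least 0.6. This is a fair reason to rate the point as minor. It is not a reason to leave inconsistent figures in place.

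A reader might also infer that the dropout allowance brings the study down to 85% power. Neither the documents nor the calculations support this. That figure belongs to the Spearman test, rests on an assumed bivariate normal distribution, and mostly reflects sizing the study on Pearson's r while testing with Spearman's coefficient.

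**Conclusion.** Wrong as written, and minor. Section 13.3 applies its 20% allowance to the wrong base. If dropout reaches 20% with 30 enrolled, 24 children remain against a stated requirement of 25. The conventional inflated figure is 32, two more than stated.

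The cost in power is 1.4 points by the formula that reproduces the plan's 25. For the Pearson t-test under bivariate normal data, power stays at about 90%. The conclusion about the count rests only on the section's own numbers and on reading 25 as the number to be analysed, which the reproduced formula supports. It does not show that the study is materially underpowered because of the dropout allowance.

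A larger inconsistency lies next to this one. The synopsis anticipates 20 children, which is below 25 before any loss. Power at 20 is Φ(0.6931 × √17 − 1.960) = 81.5% by the same formula, and a 20% loss would leave 16. That is not a result of the dropout arithmetic, but correcting 30 to 32 would leave it untouched.

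**What to change.** Restate section 13.3 so that the requirement, dropout rate, target and power agree. Any one of these would do:

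- keep 30, and state that 20% dropout leaves 24 evaluable with about 89% power by the plan's formula;
- keep 30, and state that it preserves 25 only if dropout does not exceed 5/30 = 16.7%;
- give the inflated figure as 32 (25/0.8 = 31.25), within the existing ceiling of 40.

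In the same rewrite, reconcile the target with the 20 anticipated in the synopsis and state the power expected at that enrolment. The choice between Pearson and Spearman for the power statement should be dealt with as its own point.

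The cost is a change of wording. No visit, procedure or analysis changes, and under the first two options one stated figure becomes slightly less favourable. As a change to protocol text it would go to the CHR under section 15.1, and section 13 already provides for noting changes to the plan on the registry.

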14 DATA COLLECTION, RETENTION AND MONITORING

14.1 Data Collection Instruments

This study will take place at Oak Hill School, where we have established an ongoing outcomes study that uses a web-based platform for data entry for parents and teachers. This platform is secure and has been reviewed for adequacy by the UCSF CHR (#13-11086). Data gathered for the study will be electronically coded into a password-protected database. All uploaded files will be stored in a database not in the server's file system, and the storage format will be encrypted. We will use the same secure platform for all data collection for the current study.

14.2 Data Quality Control and Reporting

All data entered in this on-line system undergoes a rigorous quality control evaluation and pre-specified logic checks. All entries are date and time stamped, and any modifications to study data are flagged – the editor and time/day of edits are also recorded. As a result, the study database is cleaned continuously and will be ready for analysis at the completion of the last study subject visit.

14.3 Archival of Data

The database is safeguarded against unauthorized access by established security procedures; appropriate backup copies of the database and related software files is maintained.

14.4 Availability and Retention of Investigational Records

All study data is available, as need and required, for review by appropriate regulatory authorities. In this case, the UCSF CHR is the responsible regulatory authority. A file for each subject will be maintained and will include the signed Informed Consent and copies of all source documentation related to that subject. The Investigator ensures the reliability and availability of source documents from which the information on the CRF was derived.

14.5 Subject Confidentiality

All study forms containing PHI are kept in a secure database (named “eBit” for Evidence-Based Intervention and Treatment) that meets FDA criteria for electronic database security.

In eBit, only UCSF study coordinators are able to create online parent and teacher accounts, which are password-protected. Data gathered for the study will be electronically coded into a password-protected database. All uploaded files onto eBit will be stored in a database not in the server's file system, and the storage format will be encrypted. eBit uses a separate platform to handle the PHI (including parent's email addresses) that will then communicate directly with Oak Hill platforms. This will keep the PHI separate from the actual health data and will meet all the IRB and HIPPA requirements that eBit and the UCSF IT group have agreed upon.

eBit is deployed on the Microsoft Azure secure cloud platform, which, according to their website, uses “industry-standard encrypted transport protocols between user devices and Microsoft datacenters, and within datacenters themselves.” More information about Microsoft Azure’s security can be found at the following link:

<https://www.microsoft.com/en-us/TrustCenter/Security/default.aspx> . This is the same server that was used in our previously approved, and still active, CHR application for our Oak Hill School outcomes study. The UCSF IT group has reviewed the terms of this web platform and has ensured that it meets all data security requirements.

15 ADMINISTRATIVE, ETHICAL, REGULATORY CONSIDERATIONS

The study will be conducted according to the Declaration of Helsinki, Protection of Human Volunteers (21 CFR 50), Institutional Review Boards (21 CFR 56), and Obligations of Clinical Investigators (21 CFR 312).

15.1 Protocol Amendments

Any amendment to the protocol will be written by the Investigator and submitted to the UCSF CHR. Protocol amendments will not be implemented without prior written approval from the UCSF CHR except as necessary to eliminate immediate safety hazards to patients. A protocol amendment intended to eliminate an apparent immediate hazard to patients may be implemented immediately, provided the UCSF CHR is notified within five working days.

15.2 Institutional Review Boards and Independent Ethics Committees

The protocol and consent form will be reviewed and approved by the UCSF CHR prior to study initiation. Serious adverse experiences regardless of causality will be reported to the UCSF CHR in accordance with the standard operating procedures.

The UCSF CHR’s written unconditional approval of the study protocol and the informed consent form will be in the possession of the Investigator before the study is initiated.

Protocol and/or informed consent modifications or changes will not be initiated without prior written UCSF CHR approval except when necessary to eliminate immediate hazards

to the patients or when the change(s) involves only logistical or administrative aspects of the study. Such modifications will be submitted to the UCSF CHR and written verification that the modification was submitted and subsequently approved will be obtained.

15.3 Informed Consent Form

Informed consent will be obtained in accordance with the Declaration of Helsinki, ICH GCP, US Code of Federal Regulations for Protection of Human Subjects (21 CFR 50.25[a,b], CFR 50.27, and CFR Part 56, Subpart A), the Health Insurance Portability and Accountability Act (HIPAA, if applicable), and local regulations.

The consent form generated by the Investigator (attached) must be acceptable to the UCSF CHR. The written consent document will embody the elements of informed consent as described in the International Conference on Harmonisation and will also comply with local regulations.

A properly executed, written, informed consent will be obtained from each subject prior to entering the subject into the trial. Information will be given in both oral and written form and each subject's legal representatives) will be given ample opportunity to inquire about details of the study. A copy of the signed consent form will be given to the subject's legal representative and the original will be maintained with the subject's records.

15.4 Publications

The publication or presentation of any study results will comply with all applicable privacy laws, including, but not limited to, the Health Insurance Portability and Accountability Act of 1996.

15.5 Investigator Responsibilities

By signing the Agreement of Investigator form, the Investigator agrees to:

1. Conduct the study in accordance with the protocol.
2. Personally conduct or supervise the study (or investigation).
3. Ensure that the requirements relating to obtaining informed consent and CHR review and approval meet federal guidelines, as stated in § 21 CFR, parts 50 and 56.
4. Ensure that all associates, colleagues and employees assisting in the conduct of the study are informed about their obligations in meeting the above commitments.
5. Maintain adequate and accurate records in accordance with §21 CFR 312.62.
6. Ensure that an IRB that complies with the requirements of §21 CFR part 56 will be responsible for initial and continuing review and approval of the clinical study.
7. Promptly report to the IRB all changes in the research activity and all unanticipated problems involving risks to subjects or others.
8. Seek IRB approval before any changes are made in the research study, except when necessary to eliminate hazards to the patients/subjects.

9. Comply with all other requirements regarding the obligations of clinical investigators and all other pertinent requirements listed in § 21 CFR part 312.

APPENDIX 1. SCHEDULE OF STUDY VISITS - UPDATE

	VISIT 1 Screening/Month -1	VISIT 2 Baseline/ Month 0	VISIT 3 Follow-up 1/ Month 1	VISIT 4 Follow-up 2/ Month 3	VISIT 5 Follow-up 3/ Month 4
Study Clinic Visit	X			X	
Informed Consent	X				
Assign Study ID and eBit log in	X				
Demographics	X				
Medical History	X				
Urine Sample (including sibling if consented)	X			X	
Weight	X			X	
Dispense Study Supplement	X				
Administer Study Supplement		X			
Concomitant Medication Review	X	X	X	X	X
Adverse Experiences		X	X	X	X
Parent Assessments (Online)					
SCQ		X			
ABC		X	X	X	X
SRS		X	X	X	X
PedsQL		X		X	
Teacher Assessments (Online)		Teacher will complete Weekly Progress Report every week starting at baseline to month 4			
ABC		X	X	X	X
SRS		X	X	X	X

References:

5. Rothman KJ. No adjustments are needed for multiple comparisons. *Epidemiology*. Jan 1990;1(1):43-46.
